Evaluation of Wear Experience with Dailies TOTAL1 Multifocal[®] Contact lenses in Presbyopic Adults That Have Dropped out of Contact Lens Wear

Protocol number: 2023H0245

NCT number: NCT06053463

Version 2.0

18 October 2023

Evaluation of Wear Experience with Dailies TOTAL1 Multifocal[®] Contact lenses in Presbyopic Adults That Have Dropped out of Contact Lens Wear

[name], OD MS

The Ohio State University College of Optometry Innovation in Vision and Eye care Research Group - iVERG [name] [contact]

[name], OD, PhD

ProCare Vision Centers, Inc. [name] [contact]

Purpose

The purpose of this study to explore the wear experience in Dailies TOTAL1 Multifocal[®] contact lenses (Alcon, Fort Worth, TX, USA) in presbyopic adults who have previously dropped out of contact lens wear.

Study Overview

This open-label study is of presbyopic adults that have dropped out of contact lens wear. Participants whose habitual vision correction device is spectacles will be fit into Dailies TOTAL1 Multifocal[®] contact lenses. Participants will be assessed after 1 week of wear at a follow-up visit (Visit 2) to confirm a successful contact lens fit. Refitting will occur if necessary. Participants will return for a final visit after 4 weeks of wear that will include an Overall Wear Experience Survey.

Background and Rationale

Soft daily wear contact lenses are used by an estimated 40.9 million adults in the United States.[1] Contact lenses which are worn for daily wear are considered minimal risk by the FDA, and risks to wearers are minimized by proper lens care and hygiene. Daily disposable contact lenses do not require daily cleaning and overnight storage, which reduces the required amount of time to care for contact lenses. In addition, daily disposable contact lenses are associated with less lens deposits, which decreases associated comfort issues in lens wearers, including decreasing the risk of triggering Giant papillary conjunctivitis (GPC) and/or ocular allergic responses in patients.[2] Additionally, daily disposable contact lens wearers are not likely to expose their lenses to water and tend to have better lens hygiene since these lenses do not require daily cleaning. This is reflected in a study which found less superficial punctate staining and symptoms of dryness when comparing daily disposable contact lens wear with planned replacement lenses.[3]

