Global contact lens prescribing for the first 20 years of this century show that the average age of contact lens wearers was 30.8 ± 13.9 years for males and 32.5 ± 14.3 years for females. Trend analysis for that

20 year period also revealed an increase in age of lens wearers and an incomplete provision of near contact lens corrections for contact lens wearing presbyopes.[4] The increasing age of lens wearers and the limited provision of corrections indicate an unmet need. In addition, many individuals discontinue contact lens wear once their eyes require presbyopic correction.[5] Reasons for this include dissatisfaction with comfort and/or vision[5].

Purpose

The purpose of this study is to evaluate the wear experience of people with presbyopia who previously dropped out of contact lens wear when fit with a Delefilcon A soft lens multifocal lens (Dailies TOTAL1 Multifocal, Alcon, Ft. Worth TX USA). We expect to enroll a relatively equal amount of former soft multifocal contact lens wearers who dropped out due to poor vision at distance or near and single vision wearers who dropped out due to poor near vision.

Key Endpoints

- 1. Visual Analog Scale survey of lens wear symptoms (comfort, dryness, vision) with contact lenses
- 2. Assessment of the participant's quality of life with the Dailies TOTAL1 Multifocal[®] contact lenses

Study Time Points

Visit 1 will occur to determine eligibility. The informed consent process will take place before the subject arrives on site via a phone call and REDCap e-consent. The participant will answer questions about their general and ocular health to further determine eligibility. Upon arriving, visual acuity and an assessment of ocular health will occur. Eligible subjects will complete a quality of life questionnaire via REDCap while wearing their progressive addition spectacles. A contact lens fitting will be completed to fit the participants in Dailies TOTAL1 Multifocal[®] contact lenses. The initial contact lens powers will be chosen following the manufacturer's fitting guide, and all subsequent changes will follow this guide, which is included in the appendix.

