Visit 2 will occur 1 week (±3 days) after visit 1. Participants will return to the study site wearing the study provided contact lenses to complete distance and near visual acuity. Contact lens fit and movement will be assessed and the participants will be refit if necessary. If a refit is needed, an additional Visit 2 will be scheduled. This may be repeated until satisfactory fit is achieved.

Visit 3 will occur 1 month (±3 days) after the follow-up visit. Participants will return to the study site wearing the study provided contact lenses to complete distance and near visual acuity. Contact lens fit and ocular health will be assessed. The participants will complete the Overall Wear Experience Survey.

Surveys (which will be deployed in REDCap) will include:

Overall Wear Experience Survey

0-100 Scale:

- Quality of vision while watching television
- Quality of vision while using a smart phone
- Quality of vision while using the computer
- Quality of vision while dining out
- Quality of vision while playing sports
- Quality of vision while working out
- Quality of vision while reading a book/magazine/newspaper

- Overall quality of vision while wearing study lenses
- Overall comfort while wearing study lenses
- Overall satisfaction while wearing the study lenses

Exploratory endpoints

- How willing are you to continue wearing these contact lenses after the study?
- Would you recommend the study contact lenses to a friend?

Recruitment

Potential subjects may see posters placed on bulletin boards at The Ohio State University (OSU) or local eye care offices, emails to students, faculty and staff at OSU, online or paper ads, signs on the OSU buses, StudySearch, The College of Optometry website and the Innovation in Vision and Eye Care Research Group (iVERG) website. A search of the electronic medical records of The Ohio State College of Optometry may be done to identify possible subjects who may be contacted by email or phone with information about the study. A search of The OSU College of Optometry Research Database (2017H0032) will also be completed. Word of mouth referrals by study team members to OSU employees and friends may occur. Emails to alumni of the OSU College of Optometry may be sent for local doctors to notify eligible potential subjects about the study.

Inclusion criteria:

- 1. Ability to give informed consent.
- 2. Any gender.
- 3. Any racial or ethnic origin.
- 4. At least 38 years of age or older.

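### The task-vision items do not name the study lenses and use of glasses is not recorded, so near-task ratings cannot separate vision in the lenses alone from vision with added glasses

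*Combined protocol and SAP*

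**What the plan says.** The Overall Wear Experience Survey is completed at Visit 3, about a month after the follow-up visit. Its seven task items cover television, smart phone, computer, dining out, sports, working out and reading. Two near examples are "Quality of vision while using a smart phone" and "Quality of vision while reading a book/magazine/newspaper". None of the seven says what correction is being rated. The three overall items do, for example "Overall quality of vision while wearing study lenses" and "Overall satisfaction while wearing the study lenses".

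The first of the Key Endpoints is a "Visual Analog Scale survey of lens wear symptoms (comfort, dryness, vision) with contact lenses", so vision in the lenses is what the survey is meant to measure.

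The Study Overview describes the population: "Participants whose habitual vision correction device is spectacles will be fit into Dailies TOTAL1 Multifocal". At Visit 1 they answer the quality-of-life questionnaire in progressive addition spectacles. Under Purpose, roughly half are expected to be "single vision wearers who dropped out due to poor near vision". The rest are former multifocal wearers who stopped because of poor vision at distance or near.

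Distance and near acuity are measured in the study lenses at Visits 2 and 3. No section sets or records wear time, or asks about glasses used over or in place of the lenses. Results are to be reported with descriptive statistics only.

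**The concern.** Near vision is a main reason these people gave up contact lenses, so near performance is a central question of the study. All participants have spectacles as their usual correction. Someone whose near vision in the multifocal is inadequate has an obvious recourse: readers over the lenses, or a change to spectacles for the task. If that person then rates reading or phone vision, the item as listed does not tell them to leave out the help they had from glasses.

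Those with the poorest near vision in the lens have most reason to use glasses. A plausible result is that near-task scores look better than the lens alone would earn. The study has one arm and plans no comparison, so the item summaries themselves are the finding, and a reader could not tell from them whether this had happened.

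**Working it through.** The plan states no figure for this point, so the check is a count of items, a search for data capture, and an illustration on assumed inputs.

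**1. Which items name the correction** (survey list under Study Time Points)

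| Group | Items | Name the study lenses |
|---|---|---|
| Task vision | 7 | 0 |
| Overall vision, comfort, satisfaction | 3 | 3 |
| All 0-100 items | 10 | 3 |

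The anchoring phrase was available to the authors and appears only on the overall items.

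**2. Which task items are exposed.** Smart phone, computer and reading are near or intermediate tasks, and dining out is partly so. Reading glasses matter little for television, sports and working out. The problem is therefore concentrated in three to four of the seven items.

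**3. What is recorded about glasses.** The visit descriptions, the survey list and the analysis section contain no record of readers over the lenses, of spectacles in their place, or of wear time. Acuity at Visits 2 and 3 shows what the lenses achieve in the clinic, not what was worn for daily tasks at home. No planned analysis links acuity to the ratings.

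**4. Illustration of size.** Let p be the share of respondents whose rating reflects glasses, and d the points by which glasses raise that rating. Then

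shift in item mean = p × d.

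The documents give neither p nor d. Every input below is an assumption.

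| p | d | Shift (points on 0-100) |
|---|---|---|
| 0.10 | 10 | 0.10 × 10 = 1 |
| 0.20 | 20 | 0.20 × 20 = 4 |
| 0.20 | 30 | 0.20 × 30 = 6 |
| 0.40 | 30 | 0.40 × 30 = 12 |

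The table shows how the shift depends on p and d and does not estimate the bias. The trial data could not narrow the range, because p is not collected.

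**The case against.** There is a fair case that the context already settles what is rated. The survey's title concerns wear experience, the endpoint specifies vision with contact lenses, and the task items share a list with three that name the study lenses. Participants also arrive at Visit 3 wearing the lenses. Rating one's spectacles in such a survey would be a strained reading. This stands in large part and makes ratings of spectacles alone less likely. It does not deal with readers worn over the lenses: that person is wearing the study lenses and can truthfully give a high score.

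The protocol lists item content, not the REDCap screens, so an instruction naming the lenses may exist. That is also fair. None is shown, and an instruction that named the lenses would still leave glasses use unrecorded.

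A reader might infer that failure of the lens at near would be hidden. The documents do not support that. Near acuity is measured in the lenses, and the items on overall vision, satisfaction, willingness to continue and recommendation all refer to the study lenses. Poor near performance could show in any of them. They are a partial check, because none isolates everyday near tasks in the lenses alone.

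A reader might also infer a known upward bias of several points. Neither direction nor size is established. Someone who needs readers over a multifocal may mark reading vision down for that reason. That participants will have their glasses to hand during follow-up is a reasonable inference from "Participants whose habitual vision correction device is spectacles", not something the plan states.

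Finally, this is a small descriptive study with no hypothesis or threshold at stake. That limits the consequence but does not remove the ambiguity in the near-task results.

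**Conclusion.** The point holds in a limited form. As listed, none of the seven task items names the study lenses, and glasses use during about a month of wear is not captured. The near and intermediate ratings therefore cannot separate lens-alone vision from vision with added glasses, and they may be inflated. The amount cannot be estimated from the documents; 1 to 12 points is the span of the assumed scenarios only.

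The conclusion rests on two assumptions: that the REDCap version carries no fuller instruction than the listed items, and that some participants use glasses for near tasks during the study. It does not show that scores will be inflated or that most respondents will misread the items. It is a worthwhile, inexpensive improvement to the survey and does not invalidate the study.

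**What to change.** - Word the task items, at least smart phone, computer, reading and dining out, as *while wearing the study lenses, without other glasses*. Add a response option *not done in the study lenses alone*.
- Add one Visit 3 question: how often were glasses used over, or instead of, the study lenses for phone, computer and reading (never, sometimes, often, always)? This measures glasses use and does not restrict it.
- Report that proportion beside the near-task scores for all participants, with the number choosing the *not done* option for each item.
- Do not present scores among those who never used glasses as an estimate of lens performance. Use of glasses follows from how well the lens works, so that subgroup would tend to contain the people the lens suits best.

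The cost is a change to the REDCap survey, an IRB amendment for its text, and under a minute per participant. Near-task scores may come out less favourable. If the deployed survey already carries such an instruction, quoting it in the protocol settles the wording, and only the question on glasses use and its reporting need to be added.

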This monadic study will report outcomes with descriptive statistics, and as such, no power calculation is necessary. A previous multifocal study with 20 subjects was conducted recently at this site which successfully recruited and studied presbyopic patients who wore progressive addition spectacles and fit them with multifocal lenses.

Data Management and Security

During the active stages of the study (recruitment to last measurement visit), all paperwork (consents, questionnaires and data forms) for each subject will reside in a subject folder for easy access throughout the study. The folders will reside in the limited-access research area, in a locked file drawer or cupboard. At the completion of the study or disenrollment of a subject the paperwork in the subject's folders will be reorganized into a regulatory binder (consents, W-9s) and a data binder (questionnaire and data forms) and will reside in an office in the limited-access research area. When the data analysis is completed and the study is considered complete, the binders will be stored in the secure Department or Office Clinical Research Area. Paperwork (questionnaire and data forms) for individuals who participate in the baseline visit but are not eligible to continue the study will be stored in the study regulatory binder in an office in the limited-access research area. An electronic file of potential subjects and a file of enrolled subjects with their contact information, as well as electronic files of collected data with the subject number, will reside on a limited-access shared drive with firewall and password protection and is restricted to individuals in the research team. Any electronic data files that contain PHI will be destroyed at the conclusion of the study.

Risks to Subjects and Mitigation

Although rare, a subject could experience eye pain, changes in vision, continued redness or irritation of the eye when inserting or learning to insert a contact lens. More likely transient blurring of vision (less than one minute) or mild, transient (less than a minute) stinging may occur.

Whenever wearing a contact lens, the possibility of eye pain due to scratching the eye or getting an infection is possible, but not common.

Adverse Events

All adverse events will be documented and reported under the guidelines of The Ohio State University Event Reporting guidelines, with any serious, unanticipated and related events being reported to the IRB, by the PI, within 10 days. Adverse Events information will be summarized in the annual report to the IRB at the end of the study. Adverse events will be assessed and determined by [name].

Subject Dismissal

Subjects who, after study team member coaching, are not able to provide analyzable data may be dismissed from the study. Analyzable data is, for example, that which is obtained for the entire measurement interval and provides a readable eye image. Data may not be analyzable if a subject is not able to stand or move freely to utilize the equipment, to name a few possible causes. These issues are usually revealed at the screening assessment visit. Subjects who cannot provide analyzable data will be dismissed from the study. Subjects who do not keep scheduled visits within the required time frame will be dismissed from the study. Study team members will make reasonable efforts to accommodate subjects' schedules.

Protocol Violations, Discontinuation

In the event that a member of the study team or a representative of sponsor becomes aware of a major protocol violation, the IRB shall be notified within 10 working days.

